4.8.2.3. Sequential Pregnancies

The number and outcome of sequential pregnancies will be noted and presented. Sequential pregnancies will be included in the analytic dataset unless they meet the exclusion criteria defined in Section 4.8.2.1.

4.8.2.4. Multiple Gestation Pregnancies

The number, type (e.g., twin, triplet), and outcome of multiple gestation pregnancies will be noted and presented. Multiple gestation pregnancies will be included in the analytic dataset unless they meet the exclusion criteria defined in Section 4.8.2.1.

4.8.3. Comparison Groups

The registry includes unexposed participants from the SABLE protocol, however, as the likely number of these participants will be small, formal comparisons of primary and secondary outcomes between belimumab exposed and unexposed participants will not be conducted.

Given the inherent difficulties in identifying a single optimal comparison cohort, several different cohorts may be used to provide background data for interpretation of data from the belimumab exposed participants in the pregnancy registry. This section describes these different cohorts, recognizing that one or more of these options may be implemented.

4.8.3.1. Population-Based Birth Defects Surveillance Programs

The Centers for Disease Control and Prevention (CDC) Metropolitan Atlanta Congenital Defects Program (MACDP) classification system will be used as the primary comparator data for defining and coding of birth defects for all registry sites. For the occurrence of birth defects, CDC MACDP data will be used for all sites as it is widely used as a comparator in pregnancy registries. The European Surveillance of Congenital Anomalies (EUROCAT) data will be used as a secondary comparison for European sites.

The primary objectives of CDC MACDP are to regularly and systematically monitor births of malformed infants to monitor changes in incidence or other unusual patterns and to develop a case registry for use in epidemiological studies. CDC MACDP actively searches for birth defects among the 50,000 annual births to residents of metropolitan Atlanta's 5 counties and abstracts medical records at all Atlanta obstetric hospitals, pediatric referral hospitals, genetics laboratories, and vital records [Correa-Villasenor, 2003]. CDC MACDP data have been used as a comparator cohort in examinations of birth defects for other pregnancy registries (acyclovir, sumatriptan, lamotrigine, and zidovudine) [Honein 1999]. The most recent CDC MACDP 5-year prevalence of 2.78% (6,945 cases with birth defects/249,999 live births) from 1999 to 2003 is deemed the most appropriate comparator birth defect data [Correa, 2007], due to lack of adequate birth defect data for the offspring of SLE mothers.

The total prevalence of birth defects overall in EUROCAT (including fetal deaths and pregnancy terminations) from 2004-2008 was 2.33% (http://www.eurocat-network.eu/). EUROCAT is a European network of population-based registries, including 43 registries in 20 countries, and it covers 29% of the European population. It started in 1979 and includes 1.5 million births per year in Europe. Its primary objectives are to provide essential epidemiological information on congenital anomalies and to act as an information and resource center to individuals and public health professionals.

4.8.3.2. External Data Sources

The registry will explore the possibility of identifying other appropriate external comparator data and continue to review the published literature to obtain background data for the pregnancy and infant outcomes evaluated in this study. It is important to note that such studies may vary in methodology, ascertainment and classification of birth defects or other pregnancy outcomes, geographic location, sample size, and other factors that could affect any formal comparisons. Therefore, quantitative comparisons between the registry and external data may be difficult to interpret. Furthermore, principal investigators for some of these studies may have expectations regarding publications and collaboration on the use of data.

4.8.3.3. Qualitative Case Analysis

A qualitative analysis of cases will be evaluated for the emergence of unique birth defects or patterns of birth defects, if warranted by our observations.

4.8.4. Essential Analyses of Belimumab-exposed Participants

A confidence interval estimation approach will be employed to descriptively compare the outcomes observed in the belimumab exposed participants of the pregnancy registry to external data. Comparisons with external SLE cohort data will be based on the observed frequency in the pregnancy registry and associated lower 95% confidence interval limit. For this registry, power was calculated using the same confidence interval estimation approach.

4.8.4.1. Adverse Pregnancy Outcomes

The registry will identify the number of cases of spontaneous miscarriages, elective terminations, stillbirths, preterm births, and SGAs; proportions of these outcomes will be calculated with 95% confidence intervals (CIs). The denominator for the proportion of spontaneous miscarriages will be those pregnancies enrolled prior to the 20th week of gestation. Because the prevalence of spontaneous miscarriages in pregnancy registries is heavily influenced by the timing of registry enrollment [Roberts, 2009], the analysis of spontaneous miscarriages will be stratified by gestational age at enrollment. Because the prevalence of preterm birth and low birth weight is elevated in multiple gestations, these cases will be excluded from the analysis of preterm birth and / or low birth weight outcomes.

Categorization of variables for stratification, such as earliest trimester of exposure, maternal age at enrollment, and gestational age at enrollment, will be described in the RAP.

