4.3. Outcome Definitions

4.3.1. Pregnancy Outcomes of Interest

The following pregnancy outcomes will be collected by the registry:

- Spontaneous miscarriage: fetal death or expulsion of products of conception prior to 20 weeks' (<20 weeks) gestation
- Live birth: the birth of a living fetus at 20 weeks' gestation or greater (\geq 20 weeks), or, if gestational age is unknown, a fetus weighing 500 g or more (\geq 500 g)
- Stillbirth: a fetal death occurring at 20 weeks' gestation or greater (≥20 weeks), or, if gestational age is unknown, a fetus weighing 500 g or more (≥500 g)
- Elective termination: voluntary interruption of pregnancy, including pregnancy termination that occurs electively, to preserve maternal health, or due to fetal abnormalities
- Preterm birth: an infant born at gestational age less than 37 weeks (<37 weeks)
- Neonatal death: an infant who after live birth expired within the first 28 days (≤28 days) of life
- Ectopic pregnancy: implantation of a conception outside of the uterus
- Molar pregnancy: a conception that results in a gestational trophoblastic tumor
- Small for gestational age (SGA): defined as an infant whose birth weight is less than the 10th percentile for the gestational age. It is based on data derived from an appropriate reference population. The registry will utilize the sex specific international growth reference standards from the International Fetal and Newborn Growth Consortium for the 21st Century (INTERGROWTH-21st) for those born at ≥33 weeks gestational age (Villar, 2014). The INTERGROWTH-21st standards are the latest available global reference standards, representing contemporary information from an international, multiethnic, diverse population and have been specifically developed for modern research. As the INTERGROWTH-21st standards are valid for infants born between 33^{0/7} and 42^{6/7} weeks gestation, SGA will be additionally classified using the reference standard endorsed by the American Congress of Obstetricians and Gynecologists (ACOG) which is applicable for the entire range of gestational age (Alexander, 1996).

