4.4. Exposure Definition

For belimumab-exposed subjects: One complete or partial dose of commercially supplied belimumab, administered within the 4 months (i.e., a period of approximately 5 belimumab terminal half-lives) prior to and /or during pregnancy, will constitute exposure. Belimumab exposure will be further categorized by earliest trimester of exposure, as described in Section 4.8.2.2.

For belimumab "unexposed" subjects: Treatment with any immunosuppressants (azathioprine, methotrexate, cyclophosphamide, mycophenolate, biologics or others) as defined in the SABLE protocol as SLE treatment, excluding belimumab (Protocol HGS1006-C1124). There must be sufficient evidence to confirm that exposure to belimumab did not occur within 4 months prior to and / or during pregnancy for a woman to be classified within this group.

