4.8.1. Belimumab Exposed Participants

The summary statistics for continuous and categorical variables to be used will be specified in the Reporting and Analysis Plan (RAP) but may include means, standard deviations, medians, minimums, maximums, percentiles, and percentages. Frequencies and proportions of adverse pregnancy outcomes, birth defects, and serious and/or

clinically significant infections in infants will be calculated along with their 95% confidence intervals.

The registry data will be used to conduct risk estimation and comparative analyses for the primary endpoint of birth defects and descriptive analyses for all secondary endpoints (i.e. pregnancy and infant outcomes). The presence of a birth defect will be summarized for registry participants with SLE who have been exposed to commercially supplied belimumab within the four months prior to and/or during pregnancy. The birth defect prevalence will be calculated as the percentage of birth defects from the total number of live births [Parker, 2010]; this approach is commonly used in other drug exposure pregnancy registries [Covington, 2004; Tomson, 2004; Holmes, 2008]. Fetal losses occurring at or after 20 gestational weeks with reported birth defects will be included in the estimation for the risk for birth defects to increase sensitivity and to allow comparison of the registry birth defect rates with the CDC MACDP and EUROCAT surveillance systems. An analysis will also be conducted to include fetal losses with reported birth defects for birth defects occurring at less than 20 gestational weeks in the calculation of risk for birth defects.

Analyses will be stratified by subgroups of interest including: timing of exposure (i.e. prior to conception and after conception or during pregnancy as well as trimester or gestational week) and level of exposure (as indicated by dose and duration of belimumab dosing); gestational age at enrollment; maternal age; and region, such as North America and Europe. Additional details on subgroup analyses will be described in the RAP. Comparisons may be made to external cohorts, if appropriate.

Primary Endpoint:

• Birth defects

Secondary Endpoints:

Other pregnancy outcomes

- Spontaneous miscarriage
- Live birth (preterm birth and SGA)
- Stillbirth
- Elective termination

Infant outcomes through age 1 year

• Serious and/or clinically significant infections

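### The pooled miscarriage proportion is biased low by late enrollment, and strata by enrollment week give no cumulative risk to 20 weeks; the dosing-duration strata also need a definition

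*Protocol*

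**What the plan says.** Section 4.3.1 defines spontaneous miscarriage as "fetal death or expulsion of products of conception prior to 20 weeks' (<20 weeks) gestation". Section 4.8.4.1 fixes the measure. For miscarriage and the other adverse pregnancy outcomes, "proportions of these outcomes will be calculated with 95% confidence intervals (CIs", and "The denominator for the proportion of spontaneous miscarriages will be those pregnancies enrolled prior to the 20th week of gestation".

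The same section gives its own caution, "Because the prevalence of spontaneous miscarriages in pregnancy registries is heavily influenced by the timing of registry enrollment", and its response: "the analysis of spontaneous miscarriages will be stratified by gestational age at enrollment". The categories are left to the Reporting and Analysis Plan (RAP). Section 4.8 names no time-to-event or delayed-entry estimate.

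Two other passages bear on the use of the figure. Section 4.6.8.1 counts a report as prospective only if it is registered before the pregnancy ends. Section 4.8.4 compares the registry with external SLE cohorts through the observed frequency and the lower end of its 95% interval.

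On exposure, Section 4.8.1 stratifies analyses by, among other things, "level of exposure (as indicated by dose and duration of belimumab dosing", and adds: "Additional details on subgroup analyses will be described in the RAP". Section 4.4 counts a dose as exposure if it was "administered within the 4 months (i.e., a period of approximately 5 belimumab terminal half-lives) prior to and /or during pregnancy, will constitute exposure". Duration itself is not defined.

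**The concern.** Miscarriage risk accrues week by week up to week 20, and women enter observation at different points on that scale. A simple proportion gives each enrollee the same weight whatever her remaining time at risk. Pregnancies lost before they could be enrolled drop out of numerator and denominator alike. Both features push the pooled proportion below the cumulative risk to 20 weeks.

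This matters because of the comparison rule in Section 4.8.4. If the observed frequency is too low, so is its lower limit, and an excess over an external cohort becomes harder to see. Fetal loss is a live question here: Section 1.1 reports 13 losses in 34 belimumab-exposed trial pregnancies with known outcome, elective terminations excluded.

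Duration of dosing raises a second problem. If it is counted within pregnancy up to the outcome, a loss at 10 weeks cannot have more than 10 weeks of it. Short duration is then partly a consequence of the loss, and long dosing can look protective when the drug does nothing.

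**Working it through.** The protocol states no figure for miscarriage or for duration strata, so there is none to reproduce. It also gives no enrollment-week distribution, loss hazard or dosing-duration distribution. Everything below is illustrative, under stated assumptions and no drug effect. Terminations and loss to follow-up are left out.

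**Late entry**

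1. Assume a weekly loss hazard h(w) = c·exp(−d·(w−5)) for weeks 5 to 19, with c chosen so that 1 − Π(1−h(w)) = 20%. Three shapes: flat (d = 0, c = 0.0148), mildly declining (d = 0.1, c = 0.0271) and early-loaded (d = 0.2, c = 0.0420).

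2. The risk still ahead of a woman who enrolls in week k is r(k) = 1 − Π(1−h(w)), the product running over weeks k to 19. For the flat hazard, r(5) = 20%, r(12) = 1 − 0.8^(8/15) = 11.2% and r(18) = 1 − 0.8^(2/15) = 2.9%.

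3. The planned proportion has expectation Σ n(k)·r(k) / Σ n(k), where n(k) is the number enrolled in week k. Let intended entry be uniform over a range of weeks, with only ongoing pregnancies enrolling, so that n(k) is proportional to survival to week k:

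| Entry weeks | Flat | Mild decline | Early-loaded |
|---|---|---|---|
| 5–8 | 18.2% | 16.9% | 15.4% |
| 5–12 | 15.8% | 13.5% | 11.2% |
| 6–19 | 10.7% | 8.1% | 5.9% |

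The true risk is 20% from week 5. From week 6 it is 18.8%, 17.8% and 16.5% for the three shapes.

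4. What the strata show: take equal numbers enrolled in each of weeks 5 to 19 and the mild decline. The pooled figure is 8.6%, the stratum entering before week 12 gives 14.1%, and the stratum entering in weeks 12 to 19 gives 3.8%. The gradient is visible, but none of the three is the 20% risk.

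5. A delayed-entry product-limit estimate, where each woman joins the risk set in her enrollment week, returns 20% whenever enrollment starts in week 5. If nobody enrolls before week 10, it returns only the risk from week 10 on: 7.2% to 13.8% across the three shapes.

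**Duration of dosing**

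6. Assume a true risk of 15% or 25%, a flat or mildly declining hazard, a planned stop week uniform over 0 to 38 and unrelated to outcome, and duration = min(planned stop, end of pregnancy). Split at 12 weeks of in-pregnancy dosing, miscarriage is about 27% to 45% with short dosing and 6% to 14% with long dosing, a risk ratio of 0.18 to 0.35 for a drug with no effect.

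7. Split at 20 weeks, long dosers have 0%, because a miscarriage is by definition over before then.

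8. Compared at a 12-week landmark among pregnancies still ongoing, the two groups agree (for example 14.2% and 14.2%), so the ratio is about 1.

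**The case against.** The strongest reply is that the protocol has already seen the problem. It names the influence of enrollment timing and stratifies for it, so a reader who infers that it offers nothing but a crude proportion would be wrong. That stands. The strata nevertheless remain conditional risks, and wide strata keep some of the bias.

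Second, the remedy could sit in the RAP, which is not at hand, without contradicting the protocol. True, but the protocol itself fixes the estimator and the denominator.

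Third, the size is assumption-driven, and wide entry may be unrealistic for the primary population. Pure prospective cases had no prenatal test before enrollment, and the glossary counts ultrasound as one, which favours early entry. This stands: with entry in weeks 5 to 8 the shortfall from 20% is about 2 to 5 points.

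Fourth, a reader might set the pooled figure against the 15–25% SLE background in Section 1.1 and expect false reassurance of a known size. The documents do not support that. The 15–25% covers all fetal loss including stillbirth, and the protocol does not say how those cohorts handled entry.

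Fifth, a reader might infer that the duration strata must make long dosing look protective. Section 4.8.1 does not define duration, exposure may precede conception under Section 4.4, and a landmark is not ruled out. The objection succeeds in making that point conditional. Extending it to preterm birth is not supported either: a preterm birth cuts dosing short far less than an early loss, and no calculation shows an effect.

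Finally, miscarriage is a secondary endpoint analysed descriptively, and Section 4.8.3.2 already warns that external comparisons may be hard to interpret. That limits the weight of the point but does not remove it.

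**Conclusion.** The point holds in a limited form. The pooled proportion in Section 4.8.4.1 understates cumulative miscarriage risk to 20 weeks whenever enrollment is spread over the weeks in which losses occur. Stratifying by enrollment week exposes the gradient but supplies no cumulative figure for the Section 4.8.4 comparison.

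The direction does not depend on the assumptions; the size does. For an assumed 20% risk from week 5, the pooled figure lies between about 6% (early-loaded hazard, entry over weeks 6 to 19) and 18% (flat hazard, entry over weeks 5 to 8). The 15–25% SLE figure is only an approximate benchmark.

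The duration point is conditional. If duration counts in-pregnancy dosing up to the outcome, stratifying miscarriage by it is immortal-time bias, with 0% by definition beyond 20 weeks. Under another definition it need not be. The primary birth-defect analysis is outside this point.

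**What to change.** Make the main miscarriage estimate a cumulative incidence to 20 weeks on the gestational-age scale, with delayed entry at enrollment, elective termination and other pregnancy-ending events as competing events, and censoring at last contact. State the earliest gestational week from which risk can be estimated, since nothing before the first enrollments is recoverable. Keep the proportions stratified by gestational age at enrollment as supportive, and use the cumulative figure with its interval for any comparison with external SLE cohorts, counted from the same starting week where possible.

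For outcomes that end pregnancy, define exposure level at a gestational-age landmark among pregnancies still ongoing, or treat it as time-varying. Say whether duration includes dosing before conception.

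The cost is small: a few sentences in Sections 4.8.1 and 4.8.4.1, matching RAP text and standard software. Due dates, outcome dates and treatment dates are already collected (Sections 4.6.2 and 4.6.3). The price is wider intervals where few women enroll early. One choice must also be written down: whether pregnancies lost to follow-up, which Section 4.6.8.3 keeps out of the primary population, contribute time at risk until last contact.

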2.2. Endpoints

Primary Endpoint:

• Birth defects

Secondary Endpoints:

Other pregnancy outcomes

• Spontaneous miscarriage

- Live birth (preterm birth and small for gestational age (SGA))
- Stillbirth
- Elective termination

Infant outcomes through age 1 year

• Serious and/or clinically significant infections

These endpoints are defined in Section 4.3 of the protocol.

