4.8.2.1. Exclusions for Analysis Purposes

Invalid cases (Section 4.6.8.5), pregnancies deemed lost to follow-up, retrospective cases, cases where participants do not have SLE, and SLE patients not exposed to belimumab will be excluded from the primary belimumab study population.

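### The multiple-gestation exclusion names low birth weight, which is not a registry outcome, and does not name SGA, which is; read literally, multiples stay in the SGA rate

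*Protocol*

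**What the plan says.** Sections 2.2 and 4.8.1 list preterm birth and SGA together, under live birth, as secondary endpoints. Section 4.8.4.1 opens by naming the outcomes whose proportions and 95% confidence intervals will be estimated: miscarriage, elective termination, stillbirth, preterm birth and SGA. Low birth weight is in none of these lists, and neither Section 4.3.1 nor the glossary defines it.

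Section 4.3.1 gives SGA as "defined as an infant whose birth weight is less than the 10th percentile for the gestational age".

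Later in the same paragraph of Section 4.8.4.1 comes a rule for multiples. The reason is "Because the prevalence of preterm birth and low birth weight is elevated in multiple gestations", and the rule is that "these cases will be excluded from the analysis of preterm birth and / or low birth weight outcomes".

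The general rule is in Section 4.8.2.4: "Multiple gestation pregnancies will be included in the analytic dataset unless they meet the exclusion criteria defined in Section 4.8.2.1". Section 4.8.2.1 lists invalid cases and pregnancies lost to follow-up, and adds that "retrospective cases, cases where participants do not have SLE, and SLE patients not exposed to belimumab will be excluded from the primary belimumab study population". Multiple gestation is not among its criteria.

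**The concern.** The exclusion is attached to one outcome that the registry analyses (preterm birth) and one that it does not (low birth weight). The planned outcome that depends on birth weight is left out. A programmer who follows the text has no instruction to remove multiples from SGA and a general instruction to keep them. A programmer who follows the presumed intent removes them. The two would report different SGA numerators and denominators from the same data.

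On the literal reading, the two paired live-birth endpoints are also handled differently: preterm birth is a singleton rate and SGA is a mixed rate. This matters most if the SGA rate is set beside an external cohort. Section 4.8.4 bases comparisons with external SLE cohorts on the observed frequency and its lower 95% limit. Multiples can move both for reasons unrelated to belimumab.

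**Working it through.** **1. What each section does with multiples**

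| Outcome | Listed as an endpoint (2.2, 4.8.1)? | Named in the 4.8.4.1 exclusion? | Multiples, read literally |
|---|---|---|---|
| Preterm birth | yes | yes | out |
| SGA | yes | no | in (default of 4.8.2.4) |
| Low birth weight | no | yes | no such analysis planned |

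This mismatch needs no assumption.

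**2. Scale available from the protocol**

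The protocol gives no figure for SGA, low birth weight or the share of multiples. Its only relevant design figures are the expected live births in Section 5, and these reproduce:

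- 500 × 0.83 × 0.75 = 311.25 (stated: 311)
- 500 × 0.95 × 0.80 = 380.0 (stated: 380)

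**3. Size of the shift, on assumed inputs**

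Let m be the share of live-born infants from multiple gestations, and p_s and p_m the SGA proportions in singletons and multiples.

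- Pooled proportion = (1 − m) × p_s + m × p_m
- Shift from the singleton rate = m × (p_m − p_s)

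The assumptions, none of them from the protocol, are m = 2-4%, p_s = 15-20% and p_m = 40-60%.

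| m | p_s | p_m | Shift (percentage points) |
|---|---|---|---|
| 2% | 20% | 40% | 0.02 × 20 = 0.4 |
| 2% | 15% | 60% | 0.02 × 45 = 0.9 |
| 4% | 20% | 40% | 0.04 × 20 = 0.8 |
| 4% | 15% | 60% | 0.04 × 45 = 1.8 |

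The range is 0.4 to 1.8 points. At the upper corner the pooled rate is 0.96 × 15% + 0.04 × 60% = 16.8%, against 15.0% in singletons.

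Wider assumptions widen the range. If multiples and singletons have the same SGA rate, the shift is 0. With m = 8%, p_s = 10% and p_m = 50%, it is 0.08 × 40 = 3.2 points.

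**4. Comparison with sampling error**

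- At 15% of 350 live births (the number that Section 5 uses for precision), the approximate 95% half-width is 1.96 × √(0.15 × 0.85 / 350) = 3.7 points. The largest shift on the main assumptions, 1.8 points, is about half of that.
- At 10% of 350, the exact 95% interval is 7.1% to 13.6%. The extreme 3.2-point case gives 13.2%, still inside it.
- The number of infants concerned runs from 0.02 × 311 ≈ 6 to 0.04 × 380 ≈ 15. The primary study population is the pure prospective subset (Section 4.8.2), so counts there would be smaller and intervals wider.

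**The case against.** The strongest reply is that the literal reading is not the natural one. The outcomes and the exclusion stand in one paragraph, and SGA is the only birth-weight outcome listed there. If low birth weight means something other than SGA, half of the exclusion acts on nothing. On that view the phrase is a loose label for SGA and multiples are already out. The default in Section 4.8.2.4 does not settle it either: the same default covers preterm birth, where Section 4.8.4.1 plainly overrides it. This reading is plausible, but it is not written, and it leads to the same change of wording.

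A reader might go further and infer that the SGA rate will be inflated by exactly the distortion that the plan set out to remove. The protocol does not support that. Its stated reason concerns preterm birth and low birth weight. SGA is already judged against gestational age, so the part of low birth weight that comes from early delivery is taken out. Whether multiples are more often SGA on the chosen references, and by how much, is not stated.

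Three further points stand. SGA is a secondary endpoint analysed descriptively, and no comparator or decision threshold is fixed for it. Section 4.8.2.4 already promises to present the number, type and outcome of multiple gestations, so their contribution should be visible. And the SGA and preterm rates would not share exactly the same infants in any case, because the INTERGROWTH-21st classification starts at 33 weeks. These points limit the consequence but do not remove the ambiguity.

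**Conclusion.** The mismatch between the exclusion rule and the endpoint list holds on the text alone. Section 4.8.4.1 names an outcome that the registry does not analyse and omits the birth-weight-based endpoint that it does, so a literal analyst keeps multiples in SGA.

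The numerical effect is likely upward, modest and not certain. The 0.4 to 1.8 points rest entirely on the assumed shares and SGA rates, and the direction rests on the assumption that multiples are more often SGA. The shift is probably inside the confidence interval. It would be wrong to read this as a demonstrated bias in the registry's results. The birth-defect endpoint and the sample size are not affected.

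The point is still worth correcting, because the rule is fixed in the protocol and can be carried out in two ways.

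**What to change.** In Section 4.8.4.1, replace low birth weight with SGA in both the reason and the exclusion, so that preterm birth and SGA are both estimated in singletons. In Section 4.8.2.4, add a cross-reference saying that the inclusion default is subject to this outcome-specific exclusion, and that SGA in multiples appears with the separate presentation already promised there.

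No new data are needed. The cost is a few infants leaving the SGA denominator: about 6 to 15 on the assumed 2-4% share and the protocol's 311 to 380 live births, and fewer in the pure prospective population.
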